part of the procedure as well as the total procedure time, and reduce the number of recurrences by long term follow-up.

Purpose:

The purpose of this study is to investigate surgical work space and surgical conditions in patients scheduled for laparoscopic umbilical, -linea alba and incisional herniotomy. The patients will act as their own control with evaluation of surgical work space and surgical conditions during both deep NMB and no NMB.

Hypothesis:

Deep NMB defined as TOF=0 and post-tetanic count (PTC) ≥ 1 , will give better surgical workspace, better surgical conditions, as well as shorter duration of surgery and reduced number of recurrences of hernias compared with no NMB.

Method:

See appendix 1, flow diagram.

Design:

Randomized, cross-over design, with blinding of patient and surgeon. Randomization is used to determine the treatment sequence (no NMB followed by deep NMB (Group A) or deep NMB followed by no NMB (Group B)) in order to blind the surgeon.

Outcomes:

Primary outcome:

Improvement of surgical workspace (rated on a 5-point scale) estimated as the difference between the workspace during deep NMB and the workspace without NMB. Ratings are performed in the same patient during stable pneumoperitoneum at 12 mmHg.

Protocol
The hernia study
September 16. 2016

Secondary outcomes: (comparing Group A with Group B)

- Surgeon's rating of surgical conditions while suturing the hernia (5-point rating scale)
- Duration of operating time (from first incision to last suture)
- Assessments if the surgical space is better, unchanged or worse when evaluating before and after the intervention
- Number of sudden contractions of the abdominal wall during operation (bucking or coughing),
- Number of insufflator alarms where pneumoperitoneum > 17 mmHg,
- Number of episodes with continuous abdominal contractions where the abdomen feels "tight" but the operation can still proceed (the intestines are gradually displaced near the inner surface of the abdominal wall).
- Number of recurrences of hernias by 2 year follow-up (separate publication). Patients will 2 years after operation receive a letter with invitation to ambulatory clinical assessment by a surgeon at Herlev Hospital or have the opportunity to receive a visit by a surgeon at their home address.

Number of patients:

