34 eligible patients allocated into an assessor-blinded randomized cross-over design: one group first receives deep NMB followed by no NMB and the other group first receives no NMB followed by deep NMB.

Protocol
The hernia study
September 16. 2016

Groups:

Group A: After intubation and placement of trocars: Bolus of saline (placebo) 6 ml. After three minutes the surgeon assesses the surgical workspace with pneumoperitoneum 12 mmHg. Bolus of rocuronium 0,6 mg/kg When TOF=0 the surgical workspace is assessed again.

Group B: After intubation and placement of trocars: Bolus of rocuronium 0.6 mg/kg When TOF=0 the surgeon assesses the surgical workspace with pneumoperitoneum 12 mmHg. Sugammadex is administered and when TOF=100% the surgical workspace is assessed again[8].

Criteria for participation:

Inclusion criteria:

Patients \geq 18 years old

Elective laparoscopic umbilical herniotomy, incisional herniotomy and linea alba herniotomy.

Can read and understand Danish

Informed consent

Exclusion criteria:

Known allergy to sugammadex, rocuronium or mivacurium

Known homozygous variants in the butyrylcholinesterase gene

Protocol
The hernia study
September 16. 2016

Severe renal disease, defined by S-creatinine > 0.200 mmol/L, GFR < 30ml/min or hemodialysis)

Neuromuscular disease that may interfere with neuromuscular data

Lactating or pregnant (Women of child bearing potential must take a urine pregnancy test at the day of the operation. The test will be provided by the hospital staff).

Indication for rapid sequence induction

Withdrawal criteria:

- In case of cancelling the operation, the patient will not receive the intervention. Data will not be available and therefore not analyzed and the patient will be considered as a "dropout".
- In case of the patient not receiving the intervention (trial medicine/placebo) after randomization, the data will not be analyzed and the patient will be considered as a "dropout".

These "dropout" patients will be disclaimed further data analysis.

Major violation:

- In case of need for increasing pneumoperitoneum to > 12 mmHg due to poor surgical conditions
- Converting to laparotomy

These will be characterized as major violations. The data will be analyzed in the intention-to-treat analysis, but excluded from the per-protocol analysis.

End of study:

When 34 patients have been evaluated considering the primary endpoint according to the intention-to-treat analysis, the study is finished.

Patient information:

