Intervention medicine is prepared in the medicine room before the operation. This is done under double control by the investigator who also performed the randomization. Labels named “project medicine” will be placed on the syringes.

Randomization group will be noted on a sheet (NMB sheet), on which other data concerning neuromuscular blockade (NMB) will also be noted. On this sheet will also be noted the quantity of rocuronium and sugammadex administered, as well as values measured with TOF-Watch. This will not be noted on the anesthesia form. After conclusion of anesthesia the NMB sheet will be placed in the accompanying envelope, which is sealed and placed in a locked drawer where only investigators of the study has

access to. If there is a need for emergency unblinding the envelope is placed in this drawer: The envelope must only be opened, if it is considered strictly necessary to know which group the patient belongs to with respect to further treatment. This will happen after agreement with the investigator responsible for the trial and the phone number of the investigator is written on the envelope. Motivation for broken seal shall be included in the Case Report Form (CRF).

At the front of the patient's case file a sheet will be placed, which states that the patient is included in the trial.

The patient will at no time during hospitalization and possible recurrences follow up (regarding recurrences) be informed about treatment group allocation. The patient may however be informed of this upon conclusion of data collection.

The surgeon, will be blinded to treatment group allocation during the operation.

The anesthesia personnel, including local investigator, who anaesthetize the patient, may during inception and operation not be blinded, because the degree of the neuromuscular block shall be adjusted.

Surgical personnel, recovery ward personnel and ward personnel will be blinded to treatment group allocation.

Perioperative treatment:

Monitoring:

The patient will be monitored with ECG, non-invasive blood pressure, oxygen saturation, sleep depth measure with BIS [BiSpectral Index], and temperature sensors.

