Inclusion of 1-2 patients per week is expected corresponding to duration of inclusion of approximately 24 months. Inclusion: Planned to go on in the period from February 2015 to February 2017. Inclusion of patients will be stopped when the desired number of patients is achieved. The trial will be counted as concluded, when the last patient has registered with the primary endpoint.

Data analysis and reporting: from April to May 2017.

Ethical considerations:

Laparoscopic herniotomy is presently conducted at Gentofte Hospital with an intraabdominal pressure of 12 mmHg and sometimes with use of a small quantity of muscle relaxant for intubation.

It is not considered an inconvenience to use large doses of muscle relaxant, as the effect of this is fully reversed by sugammadex at the end of the anesthesia. Anesthesia and surgery will follow guidelines apart from the dosage of muscle relaxants.

We think that it is justifiable that information about the use of muscle relaxants/antidotes be stored in a sealed envelope in the patient record with respect to the blinding. There is an option to break the seal on the envelope in an emergency situation. Routinely unblinding of the included patients will be done after the operation. Sugammadex is considered active in the first 24 hours, but the intervention will be considered to be over.

The possible benefit in this trial is to investigate whether deep neuromuscular blockade gives better surgical space conditions at pneumoperitoneum 12mmHg in patients > 18 years old undergoing laparoscopic umbilical, -linea alba and incisional herniotomy.

Protocol
The hernia study
September 16. 2016

Informed consent will be obtained before the patients arrive to the operation ward. We thereby wish to avoid having the patient make a decision about participation in the trial, in the stressed environment an operation ward is often experienced as for a patient before an operation. The inclusion and exclusion criteria used will ensure that we only investigate patients who will be able to tolerate being treated according to the two strategies. Intervention with respect to possible complications from this, are not unchanged either.

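### Routine unblinding after the operation conflicts with the emergency-only envelope rule and, if it means telling patients, with blinding through the two-year recurrence follow-up

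*Combined protocol and SAP*

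**What the plan says.** Two sections of the combined protocol and SAP govern who may learn the allocation after surgery.

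**Blinding section.** On patients: "The patient will at no time during hospitalization and possible recurrences follow up (regarding recurrences) be informed about treatment group allocation". The next sentence adds: "The patient may however be informed of this upon conclusion of data collection". The sealed envelope holding the NMB sheet may be opened only when knowing the group is needed for the patient's further treatment, with the responsible investigator's agreement and the reason entered in the CRF. On clinicians: "The surgeon, will be blinded to treatment group allocation during the operation", and "Surgical personnel, recovery ward personnel and ward personnel will be blinded to treatment group allocation", the latter with no end date. Anesthesia personnel are not blinded.

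**Ethical considerations section.** After explaining that drug information is kept in a sealed envelope, it says: "There is an option to break the seal on the envelope in an emergency situation". The next sentence is: "Routinely unblinding of the included patients will be done after the operation". The one after that remarks that sugammadex is regarded as active for 24 hours but that the intervention is then over.

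Elsewhere blinding is described only in general terms: "Randomized, cross-over design, with blinding of patient and surgeon" under Design, and "34 eligible patients allocated into an assessor-blinded randomized cross-over design" under Number of patients.

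Hernia recurrence at two years is one of seven listed secondary outcomes, all compared between the two groups. It is assessed clinically by a surgeon, at the hospital or at the patient's home. The Hypothesis names fewer recurrences as an expected benefit of deep NMB.

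**The concern.** One section makes opening the code an exception tied to clinical need. The other makes unblinding routine once the operation is over. Staff who followed the second would be following the protocol, and no other section says which prevails.

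What is at stake is the recurrence comparison. Each patient receives both conditions for the workspace ratings, but recurrence is a parallel-group outcome. After the second intervention Group A is under deep NMB and Group B has been reversed, so knowing the group means knowing which arm the Hypothesis favors. Recurrence depends on a surgeon's clinical judgment and on patients accepting an invitation or home visit. Knowledge of allocation could affect the judgment or the attendance.

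**Working it through.** This is mainly a comparison of text; the only arithmetic is for scale.

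**1. Routine unblinding against the envelope rule.** The unblinding sentence directly follows two sentences about the sealed envelope and breaking its seal, so the act it describes is most naturally the opening of that envelope. The Blinding section permits this only for need in further treatment, with agreement and a recorded reason. Routine opening meets none of these conditions. The conflict does not depend on who is told.

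**2. Routine unblinding against the patient rule.** There are three readings:

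- *Patients are told after surgery.* This contradicts the Blinding section, which bars telling them through recurrence follow-up.
- *Staff break the code and patients are not told.* The patient rule can still be kept, but the conflict in step 1 remains.
- *A negative was dropped.* Both conflicts disappear. The preceding sentence, which reserves seal-breaking for emergencies, fits this; the following sentence, which says the intervention is over, fits disclosure at least as well.

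The printed sentence is affirmative and does not choose between the first two.

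**3. Does another section protect the two-year assessment?** Surgeon blinding is stated only for the operation. The general descriptions under Design and Number of patients do not mention the two-year examiner. The point from which patients may be told, when data collection concludes, is not defined. The Schedule counts the trial as concluded at the last patient's primary endpoint; Ethical considerations counts it as ended after the last postoperative interview and completed CRF. Both points can precede the two-year visits.

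**4. Interval.** Unblinding falls after the operation and the recurrence invitation is sent two years after it, so allocation could be known for up to about two years before assessment.

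**5. Scale.** The documents give no expected recurrence rate, so no bias can be calculated. Assuming the 34 patients split equally and all are assessed, each group has 17, and one changed assessment moves that group's proportion by 1/17 = 5.9 percentage points.

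For illustration only, with assumed counts and the plan's own Fisher's exact test at 0.05 (two-sided):

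- 0/17 against 4/17: p = 2 × C(17,4)/C(34,4) = 2 × 2,380/46,376 = 0.103
- 0/17 against 5/17: p = 2 × C(17,5)/C(34,5) = 2 × 6,188/278,256 = 0.0445

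In groups this small, a single assessment can cross the threshold.

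**6. Outcomes not affected.** The workspace ratings and the intraoperative secondary outcomes are recorded before any postoperative unblinding.

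**The case against.** The strongest reply is that unblinding a patient is ordinary trial language for breaking that patient's code and need not mean telling the patient. The surrounding text concerns drug information, emergencies and how long sugammadex stays active, which suits a safety code-break by staff. This stands: a reader might infer that for patients the two sections cannot both be obeyed, and the documents do not support that, because a staff-only code-break would leave the patient rule intact. It does not remove the conflict with the envelope rule.

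A second reply is that the missing examiner blinding is a separate gap, and that safeguards exist. Drug quantities and TOF values are kept off the anesthesia form, the NMB sheet is sealed in a drawer open only to investigators, and the copy of the randomization list stays sealed until the study is completed. It is true that the gap would exist without the unblinding sentence and that these measures lower the risk. They do not guarantee a blinded examiner: routine unblinding would undo the sealing, and the End of study section finishes the study at the primary endpoint.

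Third, recurrence is one secondary outcome of seven, is reserved for a separate paper, and rests on clinical examination rather than patient report. This limits the weight of the point.

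A reader might also infer that the primary result is compromised, or that the number of two-year visits still pending at the 2017 analysis measures the problem. Neither follows. The ratings precede any unblinding. The analysis date is not the moment at which the disputed sentence acts, and the plan describes no passing of the list to patients or examiners.

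**Conclusion.** The wording conflict is real, and confidence in it is high: routine unblinding after surgery cannot be squared with an envelope that may be opened only for clinical need. Confidence that patients would actually be told is moderate, since a staff-only code-break or a dropped negative is possible and the text states neither.

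The consequence is confined to the two-year recurrence comparison, for which allocation could be known up to about two years ahead and no examiner blinding is stated. The size of any bias cannot be computed; the 5.9 points per altered assessment assumes 17 patients per group, all assessed. Severity is minor to moderate: one secondary outcome is exposed and the remedy is nearly free.

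**What to change.** - Reconcile Ethical considerations with Blinding. Delete or negate the routine unblinding sentence, or limit it to named staff who take no part in recurrence assessment and amend the envelope rule to match. Keep the emergency option.
- State that patients and the two-year examiner stay blinded until the recurrence assessment is complete, and that the end of data collection includes recurrence follow-up.
- Record any patient already unblinded after surgery, and report this with the recurrence results.
- Give one location for the sealed envelope. Blinding puts it in a locked drawer; Ethical considerations puts it in the patient record.

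The cost is a wording amendment and a check of records. No treatment, outcome or sample size changes, and patients learn their group no later than Blinding already implies. Rewording cannot restore blinding already lost. Inclusion was planned from February 2015 and this version is dated 16 September 2016, so patients may already have been operated on and their status should be checked.
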